8.5.2 ITT Analysis

Analysis of the secondary endpoints in 4.2.1 and 4.2.3 will follow the standard methods for analysis of randomized controlled trials as described below.

Analysis of the secondary efficacy endpoint of the total (first and recurrent) number of cardiovascular hospitalizations and all-cause death across all enrolling seasons in 4.2.1 will be analyzed using the proportional rates model by Mao and Lin (2016). In addition, the rate of recurrent cardiopulmonary hospitalization with all-cause death as competing risk will be analyzed using nonparametric and semi-parametric analyses based on the mean frequency function defined as the marginal mean of the cumulative number of cardiopulmonary hospitalizations over time subject to a terminal event of all-cause death by Ghosh and Lin (2000 and 2003).

Because of the randomization-once strategy for subjects who remain in the trial for multiple seasons, this approach will allow us to test the hypothesis that a strategy of high-dose influenza vaccine over multiple seasons will be superior to standard-dose influenza vaccination over multiple seasons, without running the risk that re-randomization would dilute a potentially cumulative effect. To examine this hypothesis, analysis of the secondary efficacy endpoint of the time to the first occurrence of all-cause death or cardiopulmonary hospitalization across all enrolling seasons will be performed as a standard ITT analysis using Kaplan-Meier method for estimation of the survival function, log-rank test, and Cox proportional hazards regression analysis, both stratified by the natural stratification factor of randomization year.

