### 10.2 Secondary Efficacy Endpoints

10.2.1 Total (first and recurrent) cardiopulmonary hospitalizations or death

10.2.2 Time to first occurrence of cardiovascular death or cardiovascular hospitalization within each enrolling season

10.2.3 Time to first occurrence of death or cardiopulmonary hospitalization across all enrolling seasons

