### 13.5 Analysis of Secondary Endpoints

Secondary endpoints will include total (first and recurrent) cardiopulmonary hospitalizations or all cause-death during the subject's entire study participation duration, the composite of cardiovascular death or cardiovascular hospitalization within each enrolling season, the composite of all-cause death or cardiopulmonary hospitalization across all enrolling seasons, and individual components of the primary endpoint, including time to all-cause death and time to

first occurrence of cardiopulmonary hospitalization. Time to composite endpoints and times to individual components of the composite endpoints will be analyzed similarly as the primary endpoint in Section 13.4 with individual components of the composite endpoints that are non-terminating events analyzed using methods for competing risks. Recurrent events analysis will be performed for recurrent non-terminating events across all enrolling seasons. For all analyses, two-sided p-values < 0.05 will be considered statistically significant. In addition, the rate of cardiopulmonary hospitalization with death as competing risk will be analyzed using nonparametric and semi-parametric analyses based on the mean frequency function defined as the marginal mean of the cumulative number of cardiopulmonary hospitalizations over time subject to a terminal event of death.

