4.2. Secondary Efficacy Endpoints

- 4.2.1. Total (first and recurrent) cardiopulmonary hospitalizations or all-cause death across all enrolling seasons
- 4.2.2. Time to first occurrence of cardiovascular death or cardiovascular hospitalization within each enrolling season
- 4.2.3. Time to first occurrence of all-cause death or cardiopulmonary hospitalization across all enrolling seasons
- 4.2.4. Time to first occurrence of individual components of the primary efficacy endpoint, i.e. cardiopulmonary hospitalization and all-cause death, within each enrolling season

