5. ANALYSIS SETS

With vaccination at enrollment into each influenza season and because the effects of vaccination last at least a calendar year, there will be no typical adherence issues. However, we expect some subjects will not be re-vaccinated according to randomization in subsequent influenza seasons. We will therefore employ a modified intention-to-treat (mITT) analysis in which events of interest will be analyzed per vaccination for each enrolling season, and primary endpoint events accrue from 2 weeks after influenza vaccination until July 31 of each enrolling season. Each subject can therefore contribute primary endpoint events and other endpoint events in multiple seasons in which they are vaccinated. As a subject's experiences from year to year may be correlated, each subject's contribution for each enrolling season may be considered correlated.

All subjects randomized will comprise the intent-to-treat (ITT) population. The usual ITT principle for analysis of randomized controlled trials will be followed for the assessment of balance in baseline data at randomization and for analysis of secondary efficacy endpoints 4.2.1, total (first and recurrent) cardiopulmonary hospitalizations or all-cause death across all enrolling seasons, and 4.2.3, time to first occurrence of all-cause death or cardiopulmonary hospitalization across all enrolling seasons.

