8. STATISTICAL METHODS

8.1 General Principles

All statistical data analyses will be performed using SAS (SAS Institute, Inc., Cary NC) and R (R Foundation for Statistical Computing, Vienna, Austria. <http://www.R-project.org>).

Analyses of efficacy and safety endpoints will employ the mITT analysis as described in Section 5, except for the analysis of baseline data and the secondary efficacy endpoints in 4.2.1, total (first recurrent) cardiopulmonary hospitalizations or all-cause death across all enrolling seasons, and in 4.2.3, time to first occurrence of all-cause death or cardiopulmonary hospitalization, both across all enrolling reason, which will employ the ITT analysis.

With the mITT analysis to efficacy and safety analysis, each subject will potentially contribute endpoints more than once over multiple influenza seasons, and endpoints in each subject may be correlated. In order to account for the intra-subject correlation over multiple influenza seasons, a robust variance estimator will be used in statistical inference. Due to the randomization-once strategy, those returning for re-vaccination following the initial vaccination after randomization constitute non-random cohorts. This may introduce bias due to potential differential survivorship and drop-out after the initial randomization.

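### SAP 8.5.2 names cardiovascular hospitalizations in the model for endpoint 4.2.1, which counts cardiopulmonary hospitalizations: probably a one-word slip, but one to correct

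*SAP*

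**What the plan says.** SAP 4.2.1 is the first-listed secondary efficacy endpoint: "Total (first and recurrent) cardiopulmonary hospitalizations or all-cause death across all enrolling seasons". The protocol lists the same endpoint in 10.2.1 as "Total (first and recurrent) cardiopulmonary hospitalizations or death".

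SAP 8.5.2 specifies two analyses for it. The first is a proportional rates model, whose outcome is given as "the total (first and recurrent) number of cardiovascular hospitalizations and all-cause death across all enrolling seasons in 4.2.1". The second uses the mean frequency function. It is specified for recurrent cardiopulmonary hospitalization, with all-cause death as the terminal event.

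Cardiovascular hospitalization appears elsewhere in SAP 4.2 as part of a separate endpoint, 4.2.2: "Time to first occurrence of cardiovascular death or cardiovascular hospitalization within each enrolling season".

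**The concern.** The sentence that tells the programmer which model to fit for 4.2.1 names a type of hospitalization that does not match 4.2.1. The following sentence returns to cardiopulmonary hospitalization, so two analyses in one section, meant for one endpoint, name different admissions.

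If the sentence were programmed as it stands, admissions with a pulmonary primary reason would not count in the model. Pulmonary admissions are part of what the trial set out to study: protocol 5.1 cites pneumonia and cardiopulmonary events among the outcomes that tended to be lower with high-dose vaccine. The result would be reported under the label of 4.2.1 without being an analysis of it. With two definitions in a signed-off plan, it would also be open to argument which result was the prespecified one.

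**Working it through.** The plan states no event count, effect size or power for 4.2.1, so there is no figure to reproduce for this endpoint. The check is a comparison of texts.

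**Step 1. Every statement of the endpoint, side by side.**

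| Place | Hospitalizations counted | Text |
|---|---|---|
| SAP 2.2.1 (objective) | cardiopulmonary | same wording as 4.2.1 |
| SAP 4.2.1 (endpoint) | cardiopulmonary | "Total (first and recurrent) cardiopulmonary hospitalizations or all-cause death across all enrolling seasons" |
| SAP 5 (analysis sets) | cardiopulmonary | "total (first and recurrent) cardiopulmonary hospitalizations or all-cause death across all enrolling seasons" |
| SAP 6 (event definition, ahead of the mITT and ITT censoring rules) | cardiopulmonary | an endpoint event is all-cause death or a cardiopulmonary admission |
| SAP 8.1 (general principles) | cardiopulmonary | "total (first recurrent) cardiopulmonary hospitalizations or all-cause death across all enrolling seasons" |
| Protocol 6.2.1 (objective) | cardiopulmonary | matches 10.2.1 |
| Protocol 10.2.1 (endpoint) | cardiopulmonary | "Total (first and recurrent) cardiopulmonary hospitalizations or death" |
| Protocol 13.5 (analysis) | cardiopulmonary | "Secondary endpoints will include total (first and recurrent) cardiopulmonary hospitalizations or all cause-death during the subject's entire study participation duration" |
| **SAP 8.5.2, proportional rates model** | **cardiovascular** | "the total (first and recurrent) number of cardiovascular hospitalizations and all-cause death across all enrolling seasons in 4.2.1" |

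Eight statements agree and one differs. SAP 1.2 (changes from the protocol) mentions only the dropped congenital heart disease substudy. SAP 1.3 (changes from the previous SAP) mentions only the weighting sensitivity analysis and the basis of the safety analysis. Neither declares a new outcome for 4.2.1.

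**Step 2. Could cardiovascular be shorthand for cardiopulmonary?** The documents keep the terms apart. SAP 4.2.2 is a separate endpoint built on cardiovascular hospitalization. The sample-size text (SAP 7, protocol 13.12) derives the effect for death or cardiovascular hospitalization and then has to assume a similar size for the cardiopulmonary composite. Protocol 2.5 has the endpoints committee decide whether the primary reason for admission was cardiac or pulmonary.

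**Step 3. What each analysis in 8.5.2 would count, read literally.**

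| | Cardiac admissions | Pulmonary admissions | Deaths |
|---|---|---|---|
| Endpoint 4.2.1 as defined | counted | counted | counted |
| Proportional rates model as worded | counted | not counted | counted |
| Mean-frequency analysis | counted | counted | terminal event, not counted |

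Neither analysis row matches the endpoint row. Changing the one word makes the second row match it. The third row differs from 4.2.1 by design, with or without the slip.

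**Step 4. How far it reaches.** The design figures rest on the primary endpoint alone. Inputs are the 9%, 8% and 7% seasonal event rates, 30% not revaccinated each season, and 30% of events being deaths, taken here to remove the subject from later seasons. The share returning for season 2 is 0.70 × (1 − 0.30 × 0.09) = 0.6811. For season 3 it is 0.6811 × 0.70 × (1 − 0.30 × 0.08) = 0.4653.

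- 2016-2017: 500 × 0.09 = 45.0
- 2017-2018: 2,933 × 0.09 + 500 × 0.6811 × 0.08 = 291.2
- 2018-2019: 2,933 × 0.09 + 2,933 × 0.6811 × 0.08 + 500 × 0.4653 × 0.07 = 440.1
- 2019-2020: 2,933 × 0.09 + 2,933 × 0.6811 × 0.08 + 2,933 × 0.4653 × 0.07 = 519.3

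The total is 1,295.6, against a stated 1,296. With 1,296 events and the final nominal level of 0.0476 (critical value 1.981), power for a hazard ratio of 0.82 is Φ(√1,296 × 0.18/1.82 − 1.981) = Φ(1.579) = 0.943, as stated. The interim fractions also follow: 336/1,296 = 0.259 and 776/1,296 = 0.599. None of these figures uses the 8.5.2 wording.

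**Step 5. Size of the effect on the rate ratio.** It would need the pulmonary share of all admissions, first and recurrent, and the treatment effect within that share. The documents give neither. The planned split of 30% deaths and 70% hospitalizations describes the primary composite and does not separate cardiac from pulmonary.

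**The case against.** The strongest reply is that the documents already settle the matter. The sentence cites 4.2.1, so it points to a definition and does not create one. SAP 6 defines the endpoint event as death or cardiopulmonary hospitalization ahead of the ITT rules that govern 8.5.2, and every other statement agrees. SAP 9 also requires two teams, one in SAS and one in R, to validate the analyses. Most of this stands: there is one plausible reading, and a careful programmer would probably find it. The validation is only partial protection, because both teams work from the same SAP and could agree on the same literal reading.

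It also stands that the harm is contained. Pulmonary admissions still count in the mean-frequency analysis and in endpoints 4.2.3 and 4.2.4. Under SAP 8.11 the other endpoints are tested at 0.05 without adjustment, so no later test depends on this one. None of those analyses replaces a count of all cardiopulmonary admissions plus deaths.

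A reader might infer several stronger things that the documents do not support:

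- *The sponsor chose to test a different outcome.* The cross-reference and the lists of changes point the other way.
- *A definite percentage of events would be lost.* No pulmonary share is given.
- *The omitted admissions are those most likely to respond to the vaccine.* Protocol 5.1 argues largely from cardiac events and lists pneumonia alongside other outcomes without ranking them.
- *The slip is what prevents comparison with the primary endpoint.* The two differ anyway: first event per season under mITT against total events across seasons under ITT.
- *Stroke and other vascular admissions would enter the model.* That depends on the endpoints committee's definitions document, which is not among the documents.

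**Conclusion.** The contradiction is real and sits in the operative model specification for a secondary endpoint. It is most likely a one-word drafting slip. As worded, the proportional rates model leaves out pulmonary admissions, and no analysis in 8.5.2 then tests 4.2.1 as defined. This conclusion rests on the wording alone and needs no assumption about event rates.

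Its reach is one model of one secondary endpoint. The primary endpoint, its type I error, the power and the interim boundaries are untouched. The size and direction of any effect on the rate ratio cannot be computed from the documents. It is a correction that should be made, not a threat to the trial's main conclusion.

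**What to change.** In SAP 8.5.2, replace *cardiovascular hospitalizations* with *cardiopulmonary hospitalizations* in the sentence that specifies the proportional rates model, and record the correction in the SAP's list of changes before any unblinded analysis. Leave the mean-frequency analysis as it is, on the understanding that it supports 4.2.1 but does not count deaths. If a total cardiovascular analysis is wanted, list it separately as exploratory.

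The cost is one word and one line in the list of changes. No new data, classification work or sample-size revision is needed.

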8.6 Analysis of the Correlative Endpoints for the Immune Response Substudy

Antibody titers at baseline and week 4, change in antibody titers from baseline to week 4, and the incidence of seroconversion and seroprotection in A/H1N1, A/H3N2 and B-type vaccine antigens and in A/H1N1, A/H3NW and B-Yamagata lineage at 4 weeks following vaccinations will be summarized with descriptive statistics such as geometric mean and standard deviation or median and IQR for quantitative measures and frequency and proportion for qualitative measures along with graphics such as box plots or empirical distribution functions and bar plots and compared between the two treatment arms using two-sample tests with robust variance to account for intra-subject correlation over multiple vaccinations.

Clinical outcomes will be compared between those with and those without overall seroconversion and seroprotection and antigen-specific seroconversion and seroprotection to A/H1N1, A/H3N2, B-Yamagata and B-Victoria vaccine antigens (for standard dose vaccine) and to A/H1N1, A/H3N2 and B-Victoria lineage (for high dose) using log-rank

tests. Cox proportional hazards regression analysis will be performed for the primary endpoint of the composite of all-cause death or cardiopulmonary hospitalization with the geometric mean titer across vaccine strains post-vaccination as a model term, instead of individual antibody titers, to avoid issues of collinearity, stratified by enrolling season, while adjusting for other covariates including treatment and other immune responses and the interaction between treatment and match for circulating B-Yamagata lineage that is included only in the standard-dose QIV (binary), based on influenza typing and subtyping data. The hazard ratio for each doubling of the geometric mean titer will be estimated along with confidence intervals from Cox proportional hazards regression analysis with robust variance estimation. Given that the traditional definition of seroprotection, namely HAI titers ≥ 40 , may be an inadequate estimate of a protective threshold during years of poor match between vaccine antigens and circulating strains, we will also assess seroprotection defined as HAI ≥ 80 , 160, and 320 as exploratory analyses.

In addition to the analysis of the clinical and immune outcomes, we will evaluate the association between antibody titers post-vaccination and subsequent hospitalizations using Poisson or negative binomial regression models to investigate the association of number of days in hospital per month on the log of the titers, controlling for treatment and other important covariates.

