## 9.4 Schedule of Time and Events Table

Measurement	Screening  Visit	Baseline Visit (August - January)	Week 1 Phone Call (+ 4 days)	Week 2-4 Visit (+ 4 days) 	During Influenza Season Phone Call	Summer Phone Call	Yrs 2 & 3 Baseline  (August - January)
Informed Consent	X						
Demographics & History 	X	X					X
Inclusion/Exclusion	X	X					X

Current Medications	X	X					X
Blood Draw 		X 		X 			X 
Vaccine Administration		X					X
Assessment of vaccine-related reactions		X	X				X
Cardiopulmonary Event Assessment				X	X	X	
Year 2&3 Visit Scheduling						X	

1. Screening and baseline procedures may be completed at one visit, followed by randomization and vaccine administration
2. History includes previous vaccinations
3. Immune endpoints at Baseline and at Week 2-4 visit (e.g., geometric mean titers post-vaccination, change in antibody titers between 2-4 weeks post-vaccination, seroconversion, seroprotection, and B-type vaccine antigens 2-4 weeks post-vaccination) will be assessed in subset of up to 3,000 subjects at participating sites.
4. Years 2 and 3 follow year one procedures after baseline visit
5. Optional additional blood draw at either Baseline or Week 2-4 visit for future research about biomarkers and genetic markers.
6. Returning subjects who elect to participate in the immune response sub-study in year 2 and 3 have sub-study blood draw

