### **13.7 Analysis of Immune Outcomes (Correlative Study Endpoints)**

Antibody titers and other immune responses such as the incidence of seroconversion and seroprotection in A/H1N1, A/H3N2 and B-type vaccine antigens will be summarized with descriptive statistics such as mean and standard deviation or median and IQR for quantitative measures and frequency and proportion for qualitative measures for baseline and week 4 post-vaccination along with graphics such as bar plots and compared between the two treatment arms using two-sample tests. Clinical outcomes will be compared between those with and those without seroconversion and seroprotection in A/H1N1, A/H3N2 and B-type vaccine antigens using log-rank tests. Cox proportional hazards regression analysis will be performed for the primary endpoint of the composite of all-cause death or cardiopulmonary hospitalization with the geometric mean titer across vaccine strains post-vaccination as a model term, instead of individual antibody titers, to avoid issues of collinearity, stratified by influenza season, while adjusting for other covariates including treatment and other immune responses and the interaction between treatment and match for circulating B (Victoria)-lineage that is included only in the standard-dose QIV (binary), based on influenza typing and subtyping data. The hazard ratio for each doubling of the geometric mean titer will be estimated along with confidence intervals from Cox proportional hazards regression models. Given that the traditional definition of seroprotection, namely HAI titers  $\geq 40$ , may be an inadequate estimate of a protective threshold during years of poor match between vaccine antigens and circulating strains, we will also assess seroprotection defined as HAI  $\geq 80$ , 160, and 320 as exploratory analyses.

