4.4. Correlative Study Endpoints for the Immune Response Substudy

- 4.4.1. Geometric mean titers post vaccination as well as at baseline
- 4.4.2. Change in antibody titers at 4 weeks post-vaccination from baseline
- 4.4.3. Seroconversion, i.e. 4-fold rise in antibody concentrations from baseline to A/H1N1, A/H3N2, and B-type vaccine antigens 4 weeks following influenza vaccination
- 4.4.4. Seroprotection, i.e. antibody titer levels $\geq 1:40$ to the A/H1N1, A/H3N2, and B-type vaccine antigens 4 weeks following influenza vaccination
- 4.4.5. Seroconversion, i.e. 4-fold rise in antibody concentrations from baseline to at least one vaccine antigen (A/H1N1, A/H3N2, or B-Victoria lineage for high dose and standard dose vaccines, and to B-Yamagata lineage for standard dose vaccine) 4 weeks following influenza vaccination
- 4.4.6. Seroprotection, i.e. antibody titer levels $\geq 1:40$ to at least one vaccine antigen (A/H1N1, A/H3N2, or B-Victoria lineage for high dose and standard dose vaccines,

and to B-Yamagata for standard dose vaccine) 4 weeks following influenza vaccination

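### SAP 8.6 leaves the pre-vaccination titer out of the between-arm comparison of antibody response, which costs precision but does not bias the randomized comparison

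*SAP*

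**What the plan says.** SAP objective 2.3.1 is to show that the higher dose gives a stronger humoral response, in mean titer after vaccination and in change from baseline. The matching endpoints in SAP 4.4 are "Geometric mean titers post vaccination as well as at baseline" (4.4.1) and "Change in antibody titers at 4 weeks post-vaccination from baseline" (4.4.2), followed by seroconversion and seroprotection.

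SAP 8.6 lists the quantitative measures as "Antibody titers at baseline and week 4, change in antibody titers from baseline to week 4". It summarizes them with "descriptive statistics such as geometric mean and standard deviation or median and IQR for quantitative measures". The arms are then "compared between the two treatment arms using two-sample tests with robust variance to account for intra-subject correlation over multiple vaccinations". Protocol 13.7 also specifies only two-sample tests, with "mean and standard deviation or median and IQR for quantitative measures" as summaries.

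Covariates appear in SAP 8.6 only in the models that relate titer to clinical outcome or to days in hospital. None is named for the comparison of titers between arms.

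Protocol 12.1.1 has each substudy participant give one sample at baseline and another two to four weeks after vaccination. Footnote 3 of Protocol 9.4 likewise places "Immune endpoints at Baseline and at Week 2-4 visit". A titer from before that season's vaccination is therefore available for every substudy record.

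**The concern.** Antibody titer after vaccination usually depends in part on titer before it. A test on the post-vaccination titer alone leaves that variation in the error term. A test on the change removes baseline with a fixed coefficient of 1, which over-corrects when the correlation is modest. A regression on baseline estimates the coefficient and does at least as well as either in large samples.

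What is at stake is the precision of the dose effect in objective 2.3.1, strain by strain. Clarity is also at stake. The SAP plans two tests of the same question, post-vaccination titer and change, and they can disagree. It also does not say on what scale change is measured. In a log-scale model that includes baseline, the treatment coefficient is the same whether the outcome is post-vaccination titer or change, so one estimate answers both.

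**Working it through.** The documents state no power, standard deviation, effect size or baseline/post correlation for the immune substudy, so there is no planned figure to reproduce. The correlations and effect size below are assumptions.

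**Inputs from the documents.** Allocation is 1:1 (SAP 3). The substudy has up to 3,000 subjects, about 1,000 per season (Protocol 12.0). Non-primary tests are two-sided at 0.05 (SAP 8.11).

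**Relative variance of the arm difference.** Let log2 titer have the same variance σ² before and after vaccination, with correlation ρ. With n per arm, each estimator has variance (2σ²/n) × k, where:

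- post-vaccination titer alone: k = 1
- change: k = 2(1 − ρ)
- adjusted for baseline: k = 1 − ρ²

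Adjustment never loses in large samples, because 1 − (1 − ρ²) = ρ² ≥ 0 and 2(1 − ρ) − (1 − ρ²) = (1 − ρ)² ≥ 0.

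| ρ (assumed) | post only | change | adjusted | reduction vs post only | reduction vs change |
|---|---|---|---|---|---|
| 0.3 | 1 | 1.40 | 0.91 | 9% | 1 − 0.91/1.40 = 35% |
| 0.5 | 1 | 1.00 | 0.75 | 25% | 25% |
| 0.7 | 1 | 0.60 | 0.51 | 49% | 1 − 0.51/0.60 = 15% |

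At ρ = 0.5 the gain is like having 1/0.75 = 1.33 times as many subjects. The change test beats the post-only test only when ρ exceeds 0.5.

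**Power illustration.** This assumes a true difference of 0.10 SD of log titer and one record per subject. The sizes are 1,500 per arm (half of the 3,000 ceiling) and 500 per arm (half of one season's 1,000).

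| ρ | 1,500 per arm: post / change / adjusted | 500 per arm: post / change / adjusted |
|---|---|---|
| 0.3 | 0.782 / 0.639 / 0.819 | 0.352 / 0.266 / 0.381 |
| 0.5 | 0.782 / 0.782 / 0.885 | 0.352 / 0.352 / 0.447 |
| 0.7 | 0.782 / 0.942 / 0.970 | 0.352 / 0.532 / 0.600 |

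**Where the gain applies.** These ratios compare analyses of the same records. Protocol 9.3.1 starts the substudy after the Vanguard year and lets subjects take part in several years. Footnote 6 of Protocol 9.4 lets returning subjects elect it in year 2 or 3. In those later seasons the pre-vaccination titer is measured after randomization and may carry the effect of the earlier assigned dose. Adjusting for it could remove part of the effect under study, and a change score shares that problem. The clean adjusted comparison is therefore limited to first on-study vaccinations.

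Let f be the share of substudy records that are first vaccinations. Treat records as independent with the same dose effect in every season. The adjusted analysis of that share then has variance (1 − ρ²)/f relative to a post-only test of all records. It is the more precise of the two when f exceeds 1 − ρ², that is 0.91, 0.75 and 0.51 at ρ = 0.3, 0.5 and 0.7. Against the change test the threshold is (1 + ρ)/2, that is 0.65, 0.75 and 0.85. The documents do not give f.

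**The case against.** The strongest reply is that nothing shows precision to be limiting. The plan sets no power target for the substudy. Protocol 5.3 reports that a comparison of 60 µg with 15 µg in 414 older adults reached p < 0.01 for both A strains and p = 0.04 for B. This substudy may reach 3,000, although that is a ceiling and the population differs. The plan also does not ignore baseline: change and seroconversion both use it, and at ρ = 0.7 adjustment removes only 15% of the variance of the change test. All of this stands. It makes the point one of efficiency on a correlative endpoint.

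Two stronger readings are tempting, and the documents support neither.

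- A reader might infer that the SAP tests an arithmetic change and summarizes it by a geometric mean, which does not exist for values at or below zero. If it did, the problem would be common: in a simulation on a two-fold dilution grid (assumed baseline geometric mean about 40, fold rise 1.5 to 4, log2 SD of change 1.0 to 2.0), 8% to 49% of subjects had a change of zero or less. But the SAP states no scale for change. Its list of summaries is illustrative, with median and IQR as the alternative. Its nearby wording is on ratio or log scales: seroconversion is a "4-fold rise in antibody concentrations from baseline to A/H1N1, A/H3N2, and B-type vaccine antigens 4 weeks following influenza vaccination", the hazard ratio is per doubling of titer, and the hospital-days model uses log titers. On a fold-rise scale the difficulty disappears. What remains is that scale and statistic are unspecified.
- A reader might infer that the unadjusted test is biased or inflates type I error. For the randomized comparison at first vaccination it does neither.

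The SAP speaks of week 4, whereas the protocol draws blood at two to four weeks plus 4 days. That spread adds noise, but nothing suggests that it differs between blinded arms.

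**Conclusion.** The point holds as a loss of precision. SAP 8.6 compares arms on titer without a baseline covariate that is measured in every substudy participant. On the same records, adjustment would cut variance by 9% to 49% against post-only and by 35% to 15% against change, for ρ from 0.3 to 0.7. That range rests on assumed correlations, equal variances on the log scale and one record pair per subject.

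Validity of the first-vaccination comparison is not in question, and the primary efficacy analysis is untouched. Whether the adjusted first-vaccination analysis also beats the planned tests pooled over all seasons depends on the share of first-vaccination records, which the documents do not give. The change is still worth making, because it costs little and replaces two unadjusted tests on an unstated scale with one defined estimate.

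**What to change.** Amend SAP 8.6 before titers are examined by arm:

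1. Analyze titers on the log2 scale.
2. For records from a subject's first on-study vaccination, make the comparison for each strain a linear model of log2 post-vaccination titer on treatment, same-season log2 pre-vaccination titer and season. Age group, CV risk group and days from vaccination to draw are optional additions; the last deals with the spread in draw day. Report the geometric mean titer ratio with its confidence interval.
3. Define change in SAP 4.4.2 as fold rise, and summarize it as geometric mean fold rise.
4. Report records from later seasons separately, without adjusting for a pre-vaccination titer drawn after an earlier study dose.
5. Keep the subject-level robust variance wherever seasons are pooled.

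The cost is SAP wording and programming, with no new visits or samples. The downside is coverage: Vanguard returnees and subjects who join the substudy in year 2 or 3 have no substudy sample from before their first study dose, so they do not enter the adjusted analysis and appear only in the later-season results.
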